#### 6.3. Other Endpoint(s)

DMB02-GSOP-RF02 7.0 Statistical Analysis Plan Template 31-Jan-2022 PFIZER CONFIDENTIAL TMF Doc ID: 98.03 Page 23 of 30

#### 6.4. Subset Analyses

No subset analyses will be performed.

# 6.5. Baseline and Other Summaries and Analyses

#### 6.5.1. Baseline Summaries

Demographics data (age, biological sex, race, ethnicity, body weight, body mass index and height) will be summarized across all participants in the safety population (as defined in Section 4) as described in Section 5.2.1 or Section 5.2.2 (as appropriate).

DMB02-GSOP-RF02 7.0 Statistical Analysis Plan Template 31-Jan-2022 PFIZER CONFIDENTIAL TMF Doc ID: 98.03 Page 24 of 30

### 6.5.2. Study Conduct and Participant Disposition

Participant evaluation groups will show end of study participant disposition by treatment and overall and will show which participants were analyzed for PK and safety, which may not be produced in one table. Frequency counts and percentages will be supplied for participant discontinuation(s) by treatment.

#### 6.5.3. Study Treatment Exposure

Not applicable.

#### 6.5.4. Concomitant Medications and Nondrug Treatments

All prior and concomitant medication(s) as well as non-drug treatment(s) will be provided in listings.

#### 6.6. Safety Summaries and Analyses

See Section 6.2.

#### 7. INTERIM ANALYSES

#### 7.1. Introduction

No interim analysis will be conducted for this study. As this is an open-label study, the sponsor may conduct unblinded reviews of the data during the course of the study for the purpose of safety and PK assessment, facilitating PK/PD modeling, and/or supporting clinical development.

#### 7.2. Interim Analyses and Summaries

Not applicable.

#### APPENDICES

# Appendix 1. PK Analyses – Example of SAS Code for mixed effects model

An example of the PROC MIXED code:

```
proc mixed data=tab.pk;
class trt subject;
model &var = trt / ddfm=KR;
random subject /subject=subject;
lsmeans trt/ diff cl alpha=0.1;
```

run;

DMB02-GSOP-RF02 7.0 Statistical Analysis Plan Template 31-Jan-2022 PFIZER CONFIDENTIAL TMF Doc ID: 98.03 Page 26 of 30

# Appendix 2. Categorical Classes for ECG and Vital Signs of Potential Clinical Concern

## **Categories for QTcF**

Degree of Prolongation	Mild (ms)	Moderate (ms)	Severe (ms)
Absolute value of QTcF	>450 and ≤480	>480 and ≤500	>500
Increase from baseline in QTcF	>30 and ≤60	>60	

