### 9.3.4.1. Electrocardiogram Analyses

Changes from baseline for the ECG parameters QT interval, heart rate, QTcF interval, PR interval, and QRS complex will be summarized by treatment and time.

The number (%) of participants with maximum postdose QTcF values and maximum increases from baseline in the following categories will be tabulated by treatment:

 Table 12.
 Safety QTcF Assessment

Degree of Prolongation	Mild (msec)	Moderate (msec)	Severe (msec)
Absolute value	>450-480	>480-500	>500
Increase from baseline		30-60	>60

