# 10.8. Appendix 8: ECG Findings of Potential Clinical Concern

# ECG Findings That May Qualify as AEs

- Marked sinus bradycardia (rate <40 bpm) lasting minutes.
- New PR interval prolongation >280 ms.
- New prolongation of QTcF to >480 ms (absolute) or by  $\geq 60$  ms from baseline.
- New-onset atrial flutter or fibrillation, with controlled ventricular response rate: ie, rate <120 bpm.
- New-onset type I second-degree (Wenckebach) AV block of >30 seconds' duration.
- Frequent PVCs, triplets, or short intervals (<30 seconds) of consecutive ventricular complexes.

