# 6.2.1.4. Electrocardiogram (ECG)

Absolute values and changes from baseline (as defined in Section 3.2.1) in QT interval, heart rate, QTcF interval, PR interval and QRS interval will be listed, and summarized by treatment and time point using sponsor reporting standards using the safety population defined in Section 4. Tables will be paged by parameter.

Mean changes from baseline for QT interval, heart rate and QTcF interval will be plotted against time point i.e., analysis visit. Corresponding individual plots of changes from baseline will also be produced for each treatment.

Maximum absolute values and changes from baseline for QTcF, PR and QRS will also be summarized descriptively by treatment using categories as defined in Appendix 2. Numbers and percentages of participants meeting the categorical criteria will be provided. All planned and unplanned post dose timepoints will be counted in these categorical summaries. All values meeting the criteria of potential clinical concern will be listed. Values meeting the categorical criteria occurring pre-dose on Day 1 during Periods 2-8, will be attributed to the

> DMB02-GSOP-RF02 7.0 Statistical Analysis Plan Template 31-Jan-2022 PFIZER CONFIDENTIAL TMF Doc ID: 98.03 Page 20 of 30

treatment from the previous Period (e.g., an occurrence pre-dose at Period 3 Day 1, will be attributed to the Period 2 treatment).

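### SAP Appendix 2 labels QTcF increases above 30 ms one severity class lower than Protocol Table 12, omits an increase of exactly 30 ms, and does not declare the change

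*SAP*

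**What the plan says.** Protocol Section 9.3.4.1 commits to a categorical QTcF table: "The number (%) of participants with maximum postdose QTcF values and maximum increases from baseline in the following categories will be tabulated by treatment". The categories are those of Table 12, under the headings "Degree of Prolongation Mild (msec) Moderate (msec) Severe (msec"). Its change row reads "Increase from baseline 30-60 >60", with the first cell, under Mild, left blank. So 30-60 ms is Moderate and >60 ms is Severe.

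SAP Section 6.2.1.4 delivers that table, drawing on Appendix 2: "Maximum absolute values and changes from baseline for QTcF, PR and QRS will also be summarized descriptively by treatment using categories as defined in Appendix". That appendix has the headings "Degree of Prolongation Mild (ms) Moderate (ms) Severe (ms"), and its change row is "Increase from baseline in QTcF >30 and ≤60 >60". Here the entries start under Mild and the last cell is blank. So >30 to ≤60 ms is Mild, >60 ms is Moderate, and nothing is Severe.

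The row for absolute values, "Absolute value of QTcF >450 and ≤480 >480 and ≤500 >500", matches Table 12 class for class.

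SAP Section 2.1, which exists to record departures from the protocol's analysis plan, mentions only the 240 mg cap and the shortened study. The version history records one change to Appendix 2, and it concerns vital signs thresholds.

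**The concern.** Two documents that govern the same safety table attach different severity words to the same size of QTcF increase. If the SAP is followed, the report will call an increase above 60 ms Moderate where the protocol said Severe, and an increase above 30 and up to 60 ms Mild where the protocol said Moderate. The shift is systematic, in the lenient direction and unexplained. ECG parameters belong to the secondary safety endpoints, and a reader who checks the report against the protocol would query the difference.

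A smaller difference does not depend on table layout. The protocol band starts at 30 ms and the SAP band starts above 30 ms.

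**Working it through.** No sample size, power or error rate is involved. The check sets the two rows side by side and classifies test values under each.

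**Rules as printed**, with x the maximum increase from baseline in ms:

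- Protocol Table 12: Moderate if 30 ≤ x ≤ 60; Severe if x > 60; Mild not used.
- SAP Appendix 2: Mild if 30 < x ≤ 60; Moderate if x > 60; Severe not used.

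Reading the protocol's lower limit as inclusive is an interpretation. Table 12 supports it: the absolute row writes its exclusive lower limits with a > sign, and the 30-60 cell has none.

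**Classification**

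| Increase (ms) | Protocol Table 12 | SAP as printed | SAP row moved one column right |
|---|---|---|---|
| 29 | none | none | none |
| 30 | Moderate | none | none |
| 31 | Moderate | Mild | Moderate |
| 45 | Moderate | Mild | Moderate |
| 60 | Moderate | Mild | Moderate |
| 61 | Severe | Moderate | Severe |
| 75 | Severe | Moderate | Severe |

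Every tested value above 30 ms is one class lower in the SAP. Moving the row restores agreement everywhere except at exactly 30 ms, which needs its own edit.

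**Effect on counts.** Let a be the number of participants with a maximum increase of exactly 30 ms, b the number above 30 and up to 60 ms, and c the number above 60 ms.

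- Protocol: Moderate = a + b, Severe = c.
- SAP: Mild = b, Moderate = c.

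The upper band holds c participants either way. The lower band differs by (a + b) − b = a. So the numbers in the table change only by those at exactly 30 ms; the rest of the difference is the column heading above them. The documents do not state the resolution at which QTcF is recorded, so how often a exceeds zero cannot be judged from them.

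**Control.** The absolute rows agree (>450 to 480, >480 to 500, >500), so the mismatch is confined to the change row.

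**The case against.** **Column position.** The label shift rests on where one blank cell sits in a table read from PDF text. The neighbouring SAP table for PR and QRS appears to have lost a row label, so extraction damage nearby is plausible. Against that, the extracted text keeps the blank cell under Mild in the protocol row, and the SAP's absolute row is intact. The shift is therefore the natural reading, but it needs a check against the PDF itself. The 30 ms difference survives whatever that check shows.

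**Permission to differ.** Protocol Section 9 lets the SAP modify the planned analyses and requires an amendment only for major changes to the primary endpoint definitions or their analyses. A deliberate regrading would be allowed. That stands, but it does not explain why nothing is declared in the section meant for such changes.

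**Small consequence.** This is descriptive tabulation in about 24 participants, with no hypothesis test or decision rule. After the Period 1 Day 1 ECG, the schedule has ECGs only on Period 3 Day 8, Period 6 Day 10 and Period 8 Day 5, plus early termination. This also stands, and it limits the importance of the point.

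**Stronger readings that the documents do not support.**

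- A reader might infer that large increases would be hidden because no increase can be labelled Severe. They would not be. Increases above 60 ms keep their own band. SAP Section 6.2.1.4 also lists absolute values and changes, plots individual changes, and lists every value meeting the criteria. Severe for an absolute QTcF above 500 ms is unchanged.
- A reader might fault the SAP for putting exactly 60 ms in the lower band, since Protocol Appendix 8 names as a possible adverse event "New prolongation of QTcF to >480 ms (absolute) or by" 60 ms or more from baseline, and Section 8.3.3 also uses 60 ms or more. But Table 12 puts 60 ms in the lower band too, so the SAP and Table 12 agree there. Section 8.3.3 governs repeat ECGs, and its 60 ms criterion also requires QTcF above 450 ms. Appendix 8 concerns adverse event recording. Neither defines tabulation classes, and no single boundary could match them and Table 12.

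**Conclusion.** The point holds as an undeclared inconsistency in severity labels between Protocol Table 12 and SAP Appendix 2. As printed, every QTcF increase above 30 ms is labelled one class milder in the SAP, and exactly 30 ms is classified in the protocol but not in the SAP.

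Its reach is limited to the labels of a descriptive secondary safety table. The primary PK analysis is untouched. On-study ECG monitoring and adverse event recording follow protocol sections that do not use Appendix 2.

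The conclusion rests on two assumptions: that the cell positions in the extracted text are those in the PDF, and that 30-60 in Table 12 includes 30. If the first fails, only the 30 ms boundary remains. If the second fails, only the labels remain.

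**What to change.** First confirm the cell positions in both tables against the PDF. Then do one of two things:

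- Move the change row of SAP Appendix 2 one column to the right and change its lower limit to include 30 ms, so that it matches Table 12: 30 to 60 ms Moderate, above 60 ms Severe.
- If the milder grading or the exclusive 30 ms limit is intended, record it in SAP Section 2.1 with a reason.

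There is no need to align these tabulation classes with the limits in Protocol Section 8.3.3 or Appendix 8. The cost is one table row and the matching output format. No new data or analysis is needed.

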## **Categories for PR and QRS**

PR (ms)	max. ≥300	
		Baseline ≤200 and max. ≥50% increase
QRS (ms)	max. ≥140	
QRS (ms) increase from baseline	≥50% increase	

## **Categories for Vital Signs**

Systolic BP (mm Hg)	min. <90	max. >200
Systolic BP (mm Hg) change from baseline	max. decrease ≥30	max. increase ≥30
Diastolic BP (mm Hg)	min. <50	max. >100
Diastolic BP (mm Hg) change from baseline	max. decrease ≥20	max. increase ≥20
Supine pulse rate (bpm)	min. <40	max. >120

Measurements that fulfill these criteria are to be listed in the report.

Abbreviation	Term
AE	Adverse Event
ALP	Alkaline Phosphatase
ALT	Alanine Transaminase
AST	Aspartate Aminotransferase
AUC	Area Under the Curve
AUCinf	Area Under the Concentration-Time Curve from time zero
	extrapolated to infinity
AUC last	Area Under the Concentration-Time Curve from time zero to the last
	measurable concentration
AUC 24	Area Under the Concentration-Time Curve from time zero to time 24
	hours
BLQ	Below the Limit of Quantitation
bpm	Beats per minute
CL	Clearance
CL/F	Apparent total body clearance
C max	Maximum observed concentration
C-CASA	Columbia-Classification Algorithm of Suicide Assessment
CCI	
CRU	Clinical Research Unit
C-SSRS	Columbia Suicide Severity Rating Scale
CSR	Clinical Study Report
CV	Coefficient of Variation
DBP	Diastolic Blood Pressure
DE	Dabigatran etexilate
dL	Deciliter
ECG	Electrocardiogram
F/U	Follow Up
HbA1c	Haemoglobin A1c
CCI	
ID	Identification
CCI	
IRC	Internal Review Committee
LFT	Liver Function Test
LLOQ	Lower Limit of Quantitation
ln	Natural log
MD	Multiple dose
mg	milligram
mmHg	Millimetres of Mercury
ms	Millisecond
Ν	Sample Size

# **Appendix 3. List of Abbreviations**

DMB02-GSOP-RF02 7.0 Statistical Analysis Plan Template 31-Jan-2022 PFIZER CONFIDENTIAL TMF Doc ID: 98.03 Page 28 of 30

Abbreviation	Term
N/A	Not Applicable
NC	Not Calculated
ND	Not Done
NS	No Sample
CCI	
PD	Pharmacodynamic(s)
РК	Pharmacokinetic(s)
PHQ-9	Patient Healthy Questionnaire 9
QD	Once a Day
QTc	corrected QT
QTcF	corrected QT (Fridericia method)
REML	Restricted Maximum Likelihood
SAP	Statistical Analysis Plan
SBP	Systolic Blood Pressure
SD	Single Dose
SoA	Schedule of Activities
TEAEs	Treatment Emergent Adverse Events
T max	Time to maximum observed concentration
t 1/2	Half life
U/L	Units per Litre
ULN	Upper Limit of Normal
$V_z/F$	Apparent volume of distribution

## Appendix 4. C-SSRS Mapped to C-CASA - Suicidal Ideation and Behavior Events and Codes

Event Code	C-CASA Event	C-SSRS Response
Suicidal Ideation		
1	Passive	"Yes" on "Wish to be dead"
2	Active: Nonspecific (no method,	"Yes" on "Non-Specific Active
	intent, or plan)	Suicidal Thoughts"
3	Active: Method, but no intent or plan	"Yes" on "Active Suicidal Ideation
		with Any Methods (Not Plan) without
		Intent to Act"
4	Active: Method and intent, but no	"Yes" on "Active Suicidal Ideation
	plan	with Some Intent to Act, without
		Specific Plan"
5	Active: Method, intent, and plan *	"Yes" on "Active Suicidal Ideation
		with Specific Plan and Intent"
Suicidal Behavior		
1	Completed suicide	"Yes" on "Completed Suicide"
2	Suicide attempt	"Yes" on "Actual Attempt"
3	Interrupted attempt	"Yes" on "Interrupted attempt"
4	Aborted attempt	"Yes" on "Aborted attempt"
5	Preparatory actions toward imminent	"Yes" on "Preparatory Acts or
	suicidal behaviors	Behavior"
Self-injurious behavior, no suicidal intent		
	Self-injurious behavior, no suicidal	"Yes" on "Has subject engaged in
	intent	Non-suicidal Self-Injurious
		Behavior?"

#### SSRS Mapped to C-CASA (Suicidality Events and Codes)

\*According to C-SSRS, the definition of *plan* includes intent (i.e., intent to complete the suicide is implicit with the concept of plan). Thus, there is no need for the category *method and plan, but no intent*.
